## **APPENDIX D**

### **Bone Treatment Convenience and Satisfaction Questionnaire** **FACIT-TS-BTCSQ – Baseline (Modified)**

For each statement, please choose the response that best describes your expectation of this treatment.

"Treatment for bone disease" means the radiation you receive to treat your bone disease only, NOT your other cancer treatments.

| Treatment for Bone Disease Expectations  | Not at All | A little bit | Some-what | Quite a bit | Very much |
|---|-------------------|---------------------|------------------|--------------------|------------------|
| I believe that my treatment for bone disease will cause me physical pain .....                    | 0                 | 1                   | 2                | 3                  | 4                |
| I believe that receiving treatment for bone disease will be inconvenient. ....                    | 0                 | 1                   | 2                | 3                  | 4                |
| I worry that my treatment for bone disease will not be effective. ....                            | 0                 | 1                   | 2                | 3                  | 4                |
| I believe that treatment for bone disease will be harmful to me. ....                             | 0                 | 1                   | 2                | 3                  | 4                |
| I believe that my treatment schedule for bone disease will be stressful to me . ....       | 0                 | 1                   | 2                | 3                  | 4                |
| I believe that my treatment schedule for bone disease will be stressful to my family ..... | 0                 | 1                   | 2                | 3                  | 4                |
| I believe that I will be bothered by side effects of treatment for bone disease .....             | 0                 | 1                   | 2                | 3                  | 4                |

## APPENDIX E

### Bone Treatment Convenience and Satisfaction Questionnaire FACIT-TS-BTCSQ – On Treatment (Modified)

#### The following to be completed by patient.

The following is a list of statements that people receiving bisphosphonate therapy have commented are important. For each statement, please choose the response that best describes your expectation of this treatment.

**"Treatment for bone disease"** means the drug(s) you receive to treat your bone disease only, NOT your other cancer treatments.

| Treatment for Bone Disease Expectations                                | Not at All | A little bit | Some-what | Quite a bit | Very much |
|--|------------|--------------|-----------|-------------|-----------|
| Treatment for bone disease takes up my time .....               | 0          | 1            | 2         | 3           | 4         |
| My treatment for bone disease takes up my family's time .....   | 0          | 1            | 2         | 3           | 4         |
| I worry about side effects from treatment for bone disease.....        | 0          | 1            | 2         | 3           | 4         |
| My treatment for bone pain causes me physical pain .....               | 0          | 1            | 2         | 3           | 4         |
| Receiving treatment for bone disease is inconvenient. ....             | 0          | 1            | 2         | 3           | 4         |
| I worry that my treatment for bone disease will not be effective. .... | 0          | 1            | 2         | 3           | 4         |

|  |   |   |   |   |   |
|--|---|---|---|---|---|
| Treatment for bone disease seems harmful to me. ....                             | 0 | 1 | 2 | 3 | 4 |
| My treatment schedule for bone disease is
stressful to me .....        | 0 | 1 | 2 | 3 | 4 |
| My treatment schedule for bone disease is
stressful to my family ..... | 0 | 1 | 2 | 3 | 4 |
| I am bothered by side effects of treatment for
bone disease.                  | 0 | 1 | 2 | 3 | 4 |

Considering your experience with treatment for bone disease to date, please respond to the following questions.

|  | No, not
at all | Yes, to
some
extent | Yes, for
the most
part | Yes,
completely |
|--|---------------------------|------------------------------------|---------------------------------------|----------------------------|
| Are you satisfied with the results of the treatment for
your bone disease so far? ..... | 0                         | 1                                  | 2                                     | 3                          |

|   | No | Maybe | Yes |
|---|-----------|--------------|------------|
| Would you recommend this treatment for bone
disease to others with your illness? ..... | 0         | 1            | 2          |
| Would you choose this treatment for bone disease
again? .....                          | 0         | 1            | 2          |

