We hypothesize that the convenience of the STAT RT workflow will result in high patient satisfaction. The FACIT-TS-BTCSQ survey has been shown to be an effective tool in measuring the satisfaction in patients being treated for metastatic bone disease (59). Therefore, we have modified this tool to suit our patient population, and we will use this survey to measure patient satisfaction at each assessment.

Toxicity will be assessed by CTCAE Version 4.0 and RTOG Late Radiation Morbidity Scoring Criteria. These are common criteria used to assess the toxicity associated with radiation therapy. The CTCAE will assess acute toxicity, and the RTOG Late Radiation Morbidity Scoring Criteria will assess late toxicity, which is defined as toxicity that occurs 3 months or more after treatment.

**Secondary Specific Aim:** Optimize the integration of commercially available and in-development software to develop the Scan-Plan-Treat STAT RT workflow.

As described in the background, this optimization will require:

- 1) rapid co-registration of diagnostic images onto MVCT simulation images for accurate contouring and treatment planning
- 2) real-time patient-specific quality assurance using CT detectors during treatment delivery
- 3) real-time patient motion tracking to ensure accurate patient setup during MVCT simulation and treatment delivery.

To implement rapid co-registration of diagnostic images onto MVCT simulation images into the workflow, we must first confirm that this image and contour-transferring method is just as accurate as the conventional method. Again, the experimental method requires rigid and deformable co-registration of

pre-contoured diagnostic image sets to MVCT simulation scans; and in the conventional method, pre-contoured diagnostic image sets are co-registered to kilovoltage CT (kVCT) simulation images, and then kVCT simulation images are co-registered to the MVCT scan. **See Figure 4.** Contours generated from these two different registration flows will be quantitatively compared as described in detail in Section 7.1.

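### The follow-up satisfaction form (Appendix E) tells patients to rate drugs, not the study radiation, so primary objective 2.1.3 would be measured on an uncertain target

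*Combined protocol and SAP*

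**What the plan says.** Section 2.1.3 makes satisfaction with the STAT RT workflow one of four primary objectives, measured with a modified FACIT-TS-BTCSQ. Section 1.5 says the tool was adapted to this population and that "we will use this survey to measure patient satisfaction at each assessment". It also gives the hypothesis: "We hypothesize that the convenience of the STAT RT workflow will result in high patient satisfaction".

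Two versions are supplied, both labelled as modified. In Appendix D (baseline), treatment for bone disease "means the radiation you receive to treat your bone disease only, NOT your other cancer treatments". In Appendix E (on treatment), the same term "means the drug(s) you receive to treat your bone disease only, NOT your other cancer treatments", and the form opens with this sentence: "The following is a list of statements that people receiving bisphosphonate therapy have commented are important". The instruction and table heading over Appendix E's first ten items ask for the patient's expectation. The last three items have their own lead-in: "Considering your experience with treatment for bone disease to date, please respond to the following questions".

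The Time and Events table (5.1) schedules one satisfaction survey before treatment and at weeks 1, 4, 8 and 12 and months 6 and 12. Criterion 3.1.11 allows bisphosphonates but does not require them. Section 7.3 plans only to report average scores. The Study Overview says follow-up questionnaires will be compared with those completed before treatment.

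**The concern.** The two forms name different treatments under the same term, and the follow-up form names the one that is not under study. The phrase excluding other cancer treatments makes this worse, because on a form that defines the rated treatment as drugs, radiation is one of the others. Appendix D was adapted to this trial; Appendix E appears to have been left part-way.

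Patients may follow the printed definition or may assume radiation is meant because they are in a radiation study. The follow-up averages could therefore be a mixture in unknown proportions. They would not answer objective 2.1.3, and they could not be set against a baseline form about radiation. The items most exposed bear directly on the hypothesis: five of the ten burden items concern time, inconvenience or schedule stress, where a continuing drug and a 2-5 fraction course could well differ.

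**Working it through.** The plan gives no figure to reproduce here. The check is a comparison of the two forms, a count, and a bounded illustration.

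**1. Is Appendix E the follow-up form?** This is an inference, because the Time and Events table cites no appendix. Appendix D is headed as the baseline version and its items are forecasts. Appendix E is the only other version, and its closing items ask about experience to date. Section 1.5 says the survey is used at each assessment. No other reading fits the documents.

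**2. The forms side by side.**

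| | Appendix D | Appendix E |
|---|---|---|
| Treatment defined as | radiation | drug(s) |
| Lead-in refers to | this treatment | bisphosphonate recipients |
| Burden items, 0-4, higher = worse | 7 | 10 |
| Direct satisfaction items, higher = better | 0 | 3 (one 0-3, two 0-2) |
| Total rated items | 7 | 13 |

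**3. How many Appendix E items depend on the definition?** Nine use the exact defined phrase. Three use a close variant: two schedule-stress items and the satisfied-with-results item. So 9 + 3 = 12 of 13 refer to treatment for bone disease. The remaining item says bone pain, for which an analgesic is also a plausible target.

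**4. How many items have a baseline counterpart?** All 7 Appendix D items appear in Appendix E, leaving 13 − 7 = 6 without one: my time, family's time, worry about side effects, satisfied, recommend, choose again. One of the seven matches is imperfect, because the physical-pain item says bone disease in D and bone pain in E.

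**5. Forms exposed.** With 30 patients and six scheduled follow-ups, 30 × 6 = 180 at most; through week 12, 30 × 4 = 120. Actual numbers will be lower, since section 5.4 expects some patients to enter hospice care first.

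**6. Why patients might rate a drug.** Some will be on bisphosphonates, the drug class the form names. Section 7.1 describes patients as needing opioids, although the eligibility list does not require it. Section 4.6 has all fractions completed within 21 days and the surveys follow treatment, so present-tense items about time and schedule suit a continuing drug better than a finished course.

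**7. Possible size.** If a share p of forms rates a drug, and d is the drug-minus-radiation difference in mean score, the item mean shifts by p × d. The documents give neither p nor d, nor the sign of d. Assuming p from 0.10 to 0.50 on a 0-4 item:

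| | p = 0.10 | p = 0.50 |
|---|---|---|
| d = 1 | 0.1 | 0.5 |
| d = 2 | 0.2 | 1.0 |

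The same formula applies to the direct satisfaction items on their shorter scales. On a 0-2 item with d = 1, the shift of 0.1 to 0.5 is 0.1/2 = 5% to 0.5/2 = 25% of the range.

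**8. A secondary point on scoring.** Section 7.3 does not say how items are combined. If all 13 raw scores were averaged, the best possible form would score (10 × 0 + 3 + 2 + 2)/13 = 7/13 = 0.54 and the worst (10 × 4 + 0)/13 = 40/13 = 3.08, with three items running against the other ten. This is missing detail, and the main point does not rest on it.

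**The case against.** The strongest reply is that little depends on this endpoint. Satisfaction is descriptive: section 7.3 plans no test, and no stopping rule or sample-size figure uses it. Patients saw the radiation definition at baseline, know they are in a radiation study, and in some cases take no bone drug they could rate. On its face the form's target is stated, as drugs; a mixture is a prediction about how patients will behave. The Brief Pain Inventory asks at each survey visit what pain treatments a patient is receiving, and a history is taken at four follow-up visits, so one could partly identify who had a drug to rate. The p × d range only restates assumed inputs. Even with corrected wording, Appendix D forecasts and Appendix E experiences are not like-for-like change scores.

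Much of this is fair as to size. The mixture is a risk, not a certainty, and the numerical range is illustrative. But if patients do follow the printed definition, the ratings concern the wrong treatment altogether, which is no better than a mixture. Knowing that a patient takes a drug does not show which treatment was rated, and section 4.4 treats concomitant medication as not applicable. A descriptive primary objective still needs an instrument that names the right treatment, and this trial has no comparator arm against which an error of this kind might cancel.

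**Conclusion.** The point holds and should be corrected before the form is used further. Appendix E contradicts both Appendix D and objective 2.1.3, and no other text in the protocol puts it right. It affects one of four primary objectives, 12 of the 13 rated items (by meaning; 9 by exact phrase), including all three direct satisfaction items, and at most 180 scheduled forms. This rests on the inference that Appendix E is the follow-up form. The size of any bias is unknown; 0.1 to 1.0 points on a 0-4 item follows only from the assumed p of 10% to 50% and d of 1 to 2 points, and its direction cannot be stated. The form as printed offers no way to estimate p, so analysis could not recover the intended measure.

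**What to change.** In Appendix E:

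- Replace the drug definition with Appendix D's radiation definition.
- Delete the sentence about bisphosphonate recipients.
- Change expectation to experience in the instruction and table heading for the ten burden items.

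In the Time and Events table, state that Appendix D is used before treatment and Appendix E afterwards. Flag any forms already completed on the present wording and report them separately.

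In section 7.3, report the ten burden items (0-4, higher = worse) apart from the satisfied (0-3), recommend (0-2) and choose-again (0-2) items, or cite the instrument's own scoring rule if one is to be used. Limit any comparison with baseline to the seven matching items, and describe it as expectation against experience.

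The cost is one reprinted form under an IRB modification, a table footnote and two or three sentences in 7.3. No extra visits or patients are needed.

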#### **4.6 Duration of Therapy**

In the absence of treatment delays due to adverse events, treatment may continue for 2 to 5 fractions depending of the clinical situation. We expect most patients to receive treatments for less than 1 week, however, all treatments will be completed within 21 days. Receiving treatment for > 21 days will be a major protocol violation. Remaining fractions will be discontinued if:

- Inter-current illness that prevent further administration of treatment
- Unacceptable adverse events
- The patient decides to withdraw from the study, OR
- General or specific changes in the patient's condition render the patient unacceptable for further treatment in the judgment of the investigator.

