## **5.0 EVALUATIONS AND ASSESSMENTS**

### **5.1 Time and Events Table**

|  | Pre-treatment | During treatment | Week 1 | Week 4 | Week 8 | Week 12 | 6-Month | 12-Month |
|--|----------------------|-------------------------|---------------|---------------|---------------|----------------|----------------|-----------------|
| Informed Consent                                   | X                    |                         |               |               |               |                |                |                 |
| History and PE                                     | X                    |                         |               | X             |               | X              | X              | X               |
| Karnofsky Performance Status                       | X                    |                         | X             | X             | X             | X              | X              | X               |
| Toxicity Evaluations                               |                      | X                       | X             | X             | X             | X              | X              | X               |
| Opiod Logbook Evaluation                           | X                    | X                       | X             | X             | X             | X              |                |                 |
| Brief Pain Inventory                               | X                    |                         | X             | X             | X             | X              | X              | X               |
| FACT-BP and FACT-G surveys                         | X                    |                         | X             | X             | X             | X              | X              | X               |
| Satisfaction and Convenience Survey                | X                    |                         | X             | X             | X             | X              | X              | X               |
| Quality Assurance                                  | X                    |                         |               |               |               |                |                |                 |
| Diagnostic Imaging (CT/MRI/PET CT)                 | X                    |                         |               |               |               |                |                |                 |

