### **7.3 Data Analyses Plans**

Treatment response as defined by International Bone Metastases Consensus Group will be determined for each patient. As described in Section 6.1.1, pain intensity as defined by the BPI and opiate use as quantified by the OMED will be used to categorize patients as having: Complete Response, Partial Response, Pain Progression, Stable Pain. At each evaluation, the patient's BPI and OMED at that visit will be compared to the pre-treatment levels. The "Worst Pain" score from the patient's BPI will be used to evaluate for treatment response. Patient response does not require a statistical analysis. The percentage of patients in each response category at each evaluation will be reported.

Patient pain will be recorded using the BPI before treatment and at designated evaluations after treatment. Pain scores before and after treatment will be compared using a Wilcoxon signed ranks test to determine if there is a statistically significant difference. Example: Pre-treatment vs. 1 week, Pre-treatment vs. 4 weeks, etc.

Analgesic use will be recorded by requiring each patient to keep a logbook of their analgesic intake. Their opiate intake for the last 72 hours will be converted to OMED at each evaluation and used in the categorization of treatment response. The difference between their OMED before and after treatment will be compared using paired two-sample t-tests.

Patients' functional status will be determined using the Karnofsky Performance Scale at each evaluation. The difference between the KPS before and after treatment will be compared using a Wilcoxon signed ranks test.

Patients' quality of life will be measured using FACT-BP and FACT-G scores at each evaluation. The difference between the FACT scores before and after treatment will be compared using a Wilcoxon signed ranks test.

Patient satisfaction will be measured using a modified version of FACT - TS – BTCSQ. No statistical analysis will be required for reporting the results. The average scores from the satisfaction survey will be reported.

To evaluate the CT detector dose calculations, the delivered radiation dose obtained using the phantom quality assurance will be compared to the exit radiation dose quality assurance calculation. The calculated dose and delivered dose for each patient will be compared using a paired two-sample t-test, and the % difference in dose will be reported.

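### The follow-up satisfaction form (Appendix E) was not adapted to a completed radiation course, so its averages do not validly measure satisfaction with STAT RT (primary objective 2.1.3)

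*Combined protocol and SAP*

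**What the plan says.** Objective 2.1.3 is to estimate satisfaction with the STAT RT workflow using a modified FACIT-TS-BTCSQ. Section 1.5 ties it to a hypothesis: the convenience of the workflow should produce high satisfaction. It adds that the tool was modified for this population and will be used at each assessment.

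There are two versions. Appendix D (baseline) defines the treatment as radiation. Appendix E (On Treatment) is the only version available for follow-up. It opens with "The following is a list of statements that people receiving bisphosphonate therapy have commented are important", and states that the treatment "means the drug(s) you receive to treat your bone disease only, NOT your other cancer treatments". Its instruction is "please choose the response that best describes your expectation of this treatment", and the table heading also refers to expectations. Ten items scored 0-4 follow, in the present tense and without a recall period, such as "Receiving treatment for bone disease is inconvenient". Three closing items (satisfied with results, would recommend, would choose again) ask about experience so far.

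In the Section 5.1 table, the row "Satisfaction and Convenience Survey" is marked at pre-treatment, weeks 1, 4, 8 and 12, and months 6 and 12. It is blank during treatment. Section 4.6 expects most courses to last under a week and says that "all treatments will be completed within 21 days". For analysis, Section 7.3 says only that "The average scores from the satisfaction survey will be reported".

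**The concern.** A form written for patients on a continuing drug is used after a short, finished course of radiation. Appendix E does not tell the patient that the radiation is the subject, and most of its items presuppose a treatment still being received. The items that bear on the convenience hypothesis are the ones that lose their referent when the course ends.

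What is at stake is whether one of four primary objectives can be interpreted. The trial is non-randomized, so no comparison group would reveal or cancel an artefact of the form. The reported averages could describe a bisphosphonate, the absence of current radiation, a remembered radiation course, or a mixture that differs between patients and visits.

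**Working it through.** The plan gives no numerical target or assumption for satisfaction, so there is no figure to reproduce. The check sets the form against the schedule.

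**1. Timing.** Inputs: maximum course 21 days (Section 4.6); six follow-up administrations (Section 5.1).
- Week 4 is 4 × 7 = day 28, and 28 > 21. Weeks 4, 8 and 12 and months 6 and 12 therefore follow the last fraction whether weeks are counted from the start or the end of treatment: 5 of 6 forms.
- Week 1 depends on the clock. The Study Overview, Section 1.1 and Section 7.1 place visits after treatment, which makes it 6 of 6. The Section 4.1 schema puts treatment at week 0 and allows it to run 1-2 weeks, so day 7 could fall within a longer course.

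**2. What the patient is asked to rate.**

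| Feature | Appendix D (baseline) | Appendix E (follow-up) |
|---|---|---|
| Treatment defined as | Radiation | Drugs |
| Introduction | No reference to drugs | Bisphosphonate recipients |
| Frame | Expectation, before treatment | Expectation, after treatment (ten items); experience so far (three items) |
| Tense of the burden items | Mainly future | Present |

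Section 3.1.11 allows bisphosphonates. A literal reader on such a drug rates the drug. A literal reader on no bone drug has nothing to rate. A reader who takes the form to mean radiation is asked at month 6 about a schedule that ended months before. None of these readings asks for a judgement of the completed STAT RT course.

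**3. Items affected.** There are 10 + 3 = 13 rated items.
- Five of the ten concern time (patient, family), convenience, or schedule stress (patient, family). These depend most on treatment being current.
- Four (worry about side effects, worry about effectiveness, perceived harm, being bothered by side effects) can keep a meaning after radiation. They may persist, or rise with late toxicity or returning pain.
- One (physical pain caused by treatment) could be read either way.
- The three closing items have a usable frame and share only the wrong treatment definition.

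**4. Can a direction be derived?** The documents contain no item-level data, so the values below are assumptions.
- *Radiation reading.* Let m be the true ten-item mean, and let a share s of patients mark zero on k items because treatment is over. Reported mean = m(1 − s·k/10), taking the same mean on every item. With m = 1, the result runs from 1 × (1 − 0.25 × 5/10) = 0.88 (s = 25%, k = 5) down to 0 (s = 100%, k = 10). With m = 2, it runs from 1.75 down to 0.
- *Drug reading.* Let a share s rate a drug with burden b. Reported mean = m(1 − s) + b·s, with s from 25% to 100%. With m = 1 and b = 2, it rises to between 1.25 and 2.0. With m = 2 and b = 1, it falls to between 1.75 and 1.0. With m = b = 1, it stays at 1.0.

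The average can move either way, so no direction follows from the documents.

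**5. Scoring.** High is worse on the ten burden items and better on the three closing items. Section 7.3 gives no rule for reversing, grouping or pooling. In a raw pooled average, a lower burden and a lower satisfaction would both reduce the score.

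**The case against.** The strongest defence is that patients and staff know what the study is about. The baseline form has already named radiation, and many patients will answer about their radiation course whatever the follow-up wording says. The three closing items ask directly about satisfaction and do not suffer from the tense problem. The objective is descriptive, with no test or threshold. Part of this stands: the closing items are less affected, and no formal decision rests on the averages. But relying on patients to override a written definition is not a measurement plan, and the convenience hypothesis depends on the items affected most.

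A reader might go further and infer that the burden items must drift to zero over the visits and make STAT RT look better than it is. The documents do not support that. Appendix E names drugs rather than radiation, so a literal reader need not mark the lowest category. The worry, harm and side-effect items can stay up or rise. Without a scoring rule, a lower raw average does not even clearly look favourable. No figure in the documents supports any particular size of shift.

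**Conclusion.** The point holds as a defect of validity with bias of unknown size and direction. At least 5 of 6 follow-up forms, and all 6 if weeks run from the end of therapy, are given after radiation has ended. Their text defines the treatment as drugs, and ten of the 13 rated items are in the present tense under an expectation heading. The five time, convenience and schedule items are affected most; the three closing items share only the wrong definition. The averages in Section 7.3 therefore cannot be taken as a measure of satisfaction with STAT RT.

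This rests on two assumptions: that Appendix E as printed is the form handed to patients at follow-up, and that at least some answer it as written. The ranges under the working rest on assumed scores and show only that the direction is open. The change should be made, because it concerns a primary objective and costs little.

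**What to change.** In Appendix E:
- define the treatment as the study radiation, as Appendix D does;
- remove the bisphosphonate introduction;
- replace expectation with experience in the instruction and the table heading;
- put the five time, convenience and schedule items in the past tense, about the completed STAT RT course. They can then be answered at every later visit, so none needs to be dropped.

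In Section 7.3:
- base objective 2.1.3 on the first form completed after the last fraction. This is safer than fixing week 1, which could fall within a longer course if weeks run from the start of treatment;
- report the burden items (high is worse) separately from the satisfaction, recommend and choose-again items (high is better).

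The cost is one more wording change to a questionnaire that has already been modified, and a few sentences in Section 7.3. No visit or question is added. Forms already collected on the present wording would have to be reported separately.
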